### Relationship to Study Drug

The relationship or association of the AE/SAE to study drug will be characterized as “related” or “not related”. An AE/SAE will be considered to be not related to the use of the study drug if any of the following criteria are met:

- An unreasonable temporal relationship between administration of the product and the onset on the AE (e.g., the event occurred either before, or too long after administration of the product for it to be considered product-related);
- A causal relationship between the product and the AE is biologically implausible (e.g., death as a passenger in an automobile accident);
- A clearly more likely alternative explanation for the AE is present (e.g., typical adverse reaction to a concomitant drug).

Adverse events will be considered “related” to the use of the study drug if none of the “not related” criteria are met. The Investigator will use clinical judgment to determine the relationship of the AE/SAE to study drug. An AE/SAE may be related to the study drug, other concomitant medications, intercurrent illness, a procedure performed in the course of the study, or another reason. Among the potential etiologies, the Investigator will make a determination based on the most likely causal relationship. Alternative causes, such as the natural history of any underlying diseases, concomitant therapy, other risk factors, and the temporal relationship of the event to the study drug will be considered. The Investigator will also take into account the Investigator’s Brochure in the causality assessment. There may be situations when an SAE has occurred and the Investigator has minimal information to include in the initial report to the Sponsor. However, the Investigator will make an assessment of causality prior to transmission of the SAE report to the Sponsor, as the causality assessment is one of the criteria used when determining regulatory reporting requirements. The Investigator may change the causality assessment in light of follow-up information, by amending the SAE report accordingly.

SAEs that are considered related (i.e., determined to be possibly, probably, or definitely related) to the investigational product by the Sponsor-Investigator will be followed until the event resolves or stabilizes. Any SAE that occurs after treatment completion, and is considered by the Sponsor-Investigator to be related to the investigational product, will be documented and reported as appropriate.

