Current therapies are inadequate. Medications have improved the prognosis of PD, but also have problematic adverse effects [Poewe W. 2006]. Since treatment of PD is often unsatisfactory and since marijuana has recently become legal and readily available in Colorado, persons with PD have been trying it. Patients have heard from the internet, support groups and other sources that marijuana is helpful. Most are doing so on their own, without the supervision or even knowledge of their neurologist. In a survey conducted in the spring of 2014 in University of Colorado Movement Disorders Center (UCMDC) clinic about 5% of 207 PD patients, average age 69, reported using marijuana [Finseth TA. et al. 2015]. In another study Katerina Venderova and colleagues reported that 25% of PD patients had taken cannabis in the General University Hospital in Prague [Venderova K, et al. 2004]. In UCMDC, about 30% of the PD patients have asked doctors during their clinic visits over the past 6 months about marijuana.

PD mostly affects the elderly, and affected persons often have cognitive, psychiatric and motor problems, such as being prone to falling. Cannabis is well documented to cause psychosis, slowness, and incoordination. Studies have also shown that chronic users have structural and functional CNS alterations [Sneider JT., et al. 2013; Matochik JA., et al. 2005; Jager G., et al. 2010; James A, et al. 2011; Battistella G., et al. 2014; Gruber SA., et al. 2005; Stone JM., et al. 2012]. Thus cannabis is expected to be risky in persons

with PD. Further, there are many components of cannabis, and the cannabis preparations being sold in Colorado vary widely in composition. There are no definitive data regarding the benefits and risks in of these various preparations in PD. Studies on safety and efficacy are greatly needed to protect this fragile Colorado population.

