### Assessment of tolerability of each dose level

Tolerability will be assessed at each dose via collection of adverse events during administration of the standardized phone script by appropriate study staff. Severity of adverse events will be graded according to the Common Terminology Criteria for Adverse Events (CTCAE), which is published by the National Cancer Institute (NCI) of the National Institutes of Health (NIH):

Grade 1: Mild; asymptomatic or mild symptoms; clinical or diagnostic observations only; intervention not indicated.

Grade 2: Moderate; minimal, local or noninvasive intervention indicated; limiting age-appropriate instrumental ADLs. Instrumental ADLs refer to preparing meals, shopping for groceries or clothes, using the telephone, managing money, etc.

Grade 3: Severe or medically significant but not immediately life-threatening; hospitalization or prolongation of hospitalization indicated; disabling; limiting self care ADLs. Self care ADLs refer to bathing, dressing and undressing, feeding self, using the toilet, taking medications, and not bedridden.

Grade 4: Life-threatening consequences; urgent intervention indicated.

Grade 5: Death related to AE.

The protocol for dose adjustments, maintenance and discontinuation based on adverse effects is as follows:

- For subjects with a grade 1 adverse event the dose will be increased by up to 5 mg/kg/day, or if they are on the maximal targeted dose (20 mg/kg/day) it will be continued.
- For subjects with a grade 2 adverse event the dose will be reduced by 5 mg/kg/day or less.
- For subjects with a grade 3 or 4 adverse event that the Investigator determines is unrelated, the dose will be continued. When the adverse event is stabilized or resolved, e.g., subject is stable after a hip fracture repair, the dose will be increased unless they are already on the maximum targeted dose.
- For subjects with a grade 3 or 4 adverse event that the Investigator determines is related the study drug will be stopped and not restarted.

The Investigator will determine relatedness as described in Section IV. C.8, and will consider the adverse event related if she determines there is at least a reasonable possibility.

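### Relatedness of adverse events is judged by inconsistent thresholds: C.8 asks for the likeliest cause, C.2 and the reporting rules for a reasonable or possible one

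*Combined protocol and SAP*

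**What the plan says.** Section IV.C.8, Relationship to Study Drug, uses a two-way label. An event is not related if any one of three criteria is met (timing, biological implausibility, or an alternative cause) and related otherwise. The third criterion reads "A clearly more likely alternative explanation for the AE is present (e.g., typical adverse reaction to a concomitant drug". The section then adds: "Among the potential etiologies, the Investigator will make a determination based on the most likely causal relationship". Among the factors to weigh it lists "Alternative causes, such as the natural history of any underlying diseases, concomitant therapy, other risk factors" and the timing of the event relative to study drug. Its closing paragraph uses other terms: "SAEs that are considered related (i.e., determined to be possibly, probably, or definitely related) to the investigational product".

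Section C.2, Assessment of tolerability of each dose level, sends the reader to C.8 for relatedness and in the same sentence says that the investigator "will consider the adverse event related if she determines there is at least a reasonable possibility". The 7-day and 15-day FDA report rules, also in C.8, are triggered by possible relatedness.

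Section C.4, Potential drug-drug interactions, expects CBD to raise the levels of some permitted drugs and to lower others. No sentence in C.8 or C.4 says how to label an event that CBD may have produced by that route.

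**The concern.** Being the likeliest cause is a harder test than being a reasonably possible one. An investigator who follows the C.8 sentence and one who follows C.2 can label the same event differently, and each can point to the protocol.

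The label has consequences. It decides which events enter the study-related adverse event frequency, the first of the four primary measures in both stages (sections IV.A and F). It decides whether a grade 3 or 4 event ends a participant's treatment, and whether an event counts towards the study stopping rule, which needs the same related event of grade 3 or higher in at least two subjects (C.7).

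Interactions are where the difference is easiest to see. C.4 describes the result of a raised rotigotine level as low blood pressure, somnolence and impulse control problems. It describes the result of lowered rasagiline, ropinirole or selegiline as worse motor signs. The first resembles a reaction to rotigotine and the second resembles Parkinson disease, and C.8 names both concomitant therapy and the underlying disease as alternative causes. In Stage 2 such events can arise only from exposure to CBD, so any that are lost come from one side of the CBD-placebo comparison (our inference).

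**Working it through.** No figure in the plan bears on this point, so the check sets the texts side by side.

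**Step 1. Which threshold governs which use of the label**

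| Use of the label | Section | Threshold stated there |
|---|---|---|
| General classification | C.8 | Three criteria, default related, then the likeliest cause |
| Grade 3-4 dose rule | C.2 | Reasonable possibility, with a pointer to C.8 |
| Grade 3-4 participant stop, both stages | C.7 | None |
| Two-subject study stop, both stages | C.7 | None |
| Study-related event frequency | IV.A, F | None |
| SAE follow-up | C.8, closing paragraph | Possibly, probably or definitely |
| Expedited FDA reports | C.8 | Possibly, or reasonably or possibly |

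The three uses with no stated threshold fall back on C.8. C.2 says that adverse events in both stages are collected and reported as C.8 describes. C.3 carries the Stage 1 escalation strategy into Stage 2 without repeating the C.2 threshold.

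**Step 2. One event under both standards**

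Take a subject on rotigotine who develops marked low blood pressure after CBD is started.

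- Timing criterion: not met.
- Implausibility criterion: not met, since C.4 gives a mechanism.
- Alternative-cause criterion: met only if rotigotine alone is judged clearly the likelier explanation. If so, the label is not related.
- If rotigotine is judged likelier, but not clearly so, the default gives related while the likeliest-cause sentence points to rotigotine. C.8 is then divided within itself.
- C.2: a raised rotigotine level caused by CBD is a reasonable possibility, so the event is related.
- SAE follow-up and expedited reporting: possibly related, if the event otherwise qualifies.

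The stated rules can therefore give opposite labels to one event.

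**Step 3. Reach**

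C.4 names these drugs whose levels CBD may raise: five benzodiazepines and zolpidem (6), clopidogrel (1), five narcotics (5), and cyclosporine A, tacrolimus, propranolol and acetaminophen (4). That is 6 + 1 + 5 + 4 = 16. Selegiline, rasagiline, ropinirole and rotigotine add 4, giving 20. The exclusion criteria bar none of them, though acetaminophen is capped at 1 gram per day. This counts drugs, not subjects or events, and says nothing about frequency.

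**Step 4. What does not depend on the label**

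The grade 1 and 2 dose rules, the sleepiness-score rule in C.2 and the liver monitoring in section D operate without it. In Stage 2, orthostatic blood pressure, SCOPA-Sleep, QUIP-RS and MDS-UPDRS are compared between treatments whatever label an event carries.

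**The case against.** The strongest reply is that the text already covers interactions. If CBD raised the other drug's level, CBD is part of the cause, so the reaction is not an alternative to it. The third criterion then fails and the default is related. Other provisions help:

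- Anti-parkinsonian medication must have been fixed for at least a month before dosing, so a new reaction after CBD starts points towards CBD, and C.8 tells the investigator to weigh timing.
- Somnolence is CBD's own most frequent reaction (21% in Table 2) and its main dose-limiting effect, so another drug is seldom clearly the likelier cause.
- C.8 requires the Investigator's Brochure to be considered, C.4 has the PI monitor for interactions, and a formal drug interaction assessment is repeated at visits.

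This stands against a stronger reading that one might infer: that C.8 channels interaction harms into the unrelated category and the dose is then raised. C.2 does say "For subjects with a grade 3 or 4 adverse event that the Investigator determines is unrelated, the dose will be continued" and "When the adverse event is stabilized or resolved, e.g., subject is stable after a hip fracture repair, the dose will be increased", and section II notes that "affected persons often have cognitive, psychiatric and motor problems, such as being prone to falling". But the dose rule sits under C.2's own lower threshold, and the hip fracture illustrates an event already judged unrelated. Nothing in the documents ties it to an interaction.

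The reply does not reconcile the thresholds. Monitoring for an interaction is not a rule for labelling one, and the likeliest-cause sentence remains in the section to which C.2 refers.

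**Conclusion.** The point holds as an inconsistency in the relatedness threshold, with interactions as one case where it can matter. C.8 permits the label not related there but does not force it. The effect falls mainly on the study-related event tabulation, on the C.7 participant stop in Stage 2, where C.2's threshold is not restated, and on the two-subject study stop.

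Its size cannot be estimated. The documents give neither how many subjects will take the affected drugs nor how far CBD will change the levels of the permitted ones, so no number of misclassified events is claimed. The conclusion rests on reading the likeliest-cause sentence as an operative instruction. If investigators in practice apply C.2's standard throughout, the effect is nil. Severity is minor to moderate; the correction is justified because it is cheap and safety is the primary aim.

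**What to change.** Make two edits in C.8.

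1. Replace the likeliest-cause sentence with C.2's standard: an event is related if there is at least a reasonable possibility that study drug caused it or contributed to it, including by raising or lowering the level of a concomitant drug.
2. Add to the third criterion that a typical reaction to a drug whose level CBD may change (C.4, Appendix 2) does not by itself meet it. The investigator still judges each event.

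A possible-interaction flag on the adverse event page would allow separate tabulation. It is optional, since that page is not in the documents and may already have such a field.

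The cost is two wording changes. If events have already been labelled, those marked not related need one re-review, starting with subjects on a listed drug. The downside is that a few events due only to the other drug will count as related, so related-event rates and related stops will rise slightly.

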### Reporting Serious Adverse Events to Regulatory Agencies

Events meeting the following criteria will be submitted to the Food and Drug Administration (FDA) as expedited IND Safety Reports according to the following guidance and timelines:

#### 7 Calendar Day Telephone or Fax Report

The Sponsor-Investigator will notify the appropriate review division at the FDA of any fatal or life-threatening adverse event that is unexpected and assessed by the Sponsor-Investigator to be possibly related to the use of the investigational product. An unexpected adverse event is one that is not already described in the investigational product’s Investigator Brochure. Such reports are to be telephoned or faxed to the appropriate review division at FDA and to the manufacturer of the investigational product within 7 calendar days of first learning of the event.

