### Unanticipated Adverse Events

An unanticipated problem is any event or information that was unforeseen and indicates that the research procedures caused harm (including physical, psychological, economic, or social harm) to participants or others or indicates that participants or others are at increased risk of harm than was previously known or recognized. An "unexpected" adverse reaction is one in which the nature or severity of which is not consistent with information in the relevant source document(s). Until source documents are amended, expedited reporting is required for additional occurrences of the reaction.

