### 15 Calendar Day Written Report

The Sponsor-Investigator will notify the appropriate review division at the FDA, in a written IND Safety Report, of any serious, unexpected AE that is considered reasonably or possibly related to the use of the investigational product.

Written IND Safety reports will include an Analysis of Similar Events in accordance with regulation 21 CFR § 312.32. All safety reports previously filed by the Sponsor-Investigator with the IND concerning similar events will be analyzed and the significance of the new report in light of the previous, similar reports commented on.

Written IND safety reports with Analysis of Similar Events will be submitted to the appropriate review division at the FDA, and the manufacturer of the investigational product within 15 calendar days of first learning of the event, using FDA Form 3500A.

Written IND Safety Reports will be submitted to the IRB(s) of record per IRB Guidelines.

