### **C.9 Risks of Study Drug:**

A review of 25 studies on the safety and efficacy of CBD did not identify significant side effects across a wide range of dosages, including acute and chronic dose regimens, using various modes of administration. [Bergamaschi M.M., et al. 2011] There are no rare but serious side effects reported. The most frequently occurring side effect was somnolence (i.e.drowsiness) (21%). Other side effects, in order of prevalence, include: fatigue (17%), diarrhea (17%), increased appetite (17%), decreased appetite (16%), and weight loss (9%). [Devinsky O, et al. 2014] Other side effects include extrapyramidal symptoms, increased prolactin levels, weight gain increased serum concentrations of antiepileptic drugs and elevated liver function tests .

Table 2 and 3 show the adverse reactions of CBD from the IB (CBD) provided by GW Research Ltd.

**Table 2.** The adverse reactions with a plausible causal relationship to purified CBD solution—reported at a daily maximum of 25 mg/kg/day

Adverse Reactions	Related causality CBD (n=213)
Most frequently (5 to 10%)	

Somnolence	44 (21%)
Fatigue	36 (17%)
Decreased appetite	31 (15%)
Diarrhoea	29 (14%)
Lethargy	12 (6%)
Increased appetite	15 (7%)
Weight increased	12 (6%)
Convulsion	11 (5%)
Weight decreased	10 (5%)
Gait disturbance	10 (5%)
Less frequently (1 to 5%)	
Drug level increased	9 (4%)
Sedation	7 (3%)

**Table 3.** Most frequently adverse reactions of purified CBD reported at 200, 400, and 800 mg/day

Adverse reactions	CBD 200 mg/day (n=7)	CBD 400 mg/day (n=6)	CBD 800 mg/day (n=7)
Diarrhoea	4 (57%)	3 (50%)	5 (71%)
Dyspepsia	0	1 (17%)	1 (14%)
Defaecation urgency	0	0	1 (14%)
Eructation	0	0	1 (14%)
Frequent bowel movements	0	0	1 (14%)
Gastritis	1 (14%)	0	0
Gastrointestinal hypermotility	0	1 (17%)	0
Vomiting	1 (14%)	0	1 (14%)
Fatigue	1 (14%)	1 (17%)	0
Product size issue	1 (14%)	0	0

Aspartate aminotransferase increased	1 (14%)	0	0
Gamma-glutamyltransferase increased	1 (14%)	0	0
Platelet count decreased	1 (14%)	0	0
Decreased appetite	1 (14%)	0	1 (14%)
Dysgeusia	0	0	1 (14%)
Headache	1 (14%)	2 (33%)	0
Pollakiuria	0	0	1 (14%)
Rash generalised	0	0	1 (14%)
Rash maculo-papular	0	0	1 (14%)

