Based on data of Epidiolex and previous studies, some side effects, such as diarrhea, weight loss, and decreased appetite, required reduction of the dose resulting in improvement of symptoms. The large majority of adverse events were mild to moderate and transient. No significant laboratory abnormalities were observed.

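### Section C.8 gives two definitions of an unexpected event, and the one inside the 7-day rule leaves out severity

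*Combined protocol and SAP*

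**What the plan says.** Three subsections of IV.C.8 use the term *unexpected*.

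- **Unanticipated Adverse Events** gives a general definition. An unexpected "adverse reaction is one in which the nature or severity of which is not consistent with information in the relevant source document(s". The next sentence links this to expedited reporting: "Until source documents are amended, expedited reporting is required for additional occurrences of the reaction". No time limit is given there.
- **7 Calendar Day Telephone or Fax Report** applies to "any fatal or life-threatening adverse event that is unexpected and assessed by the Sponsor-Investigator to be possibly related" to the investigational product. The report goes to the FDA and the manufacturer "within 7 calendar days of first learning of the event". This subsection then supplies its own definition: "An unexpected adverse event is one that is not already described in the investigational product", with the Investigator Brochure named as the reference.
- **15 Calendar Day Written Report** requires notification "of any serious, unexpected AE that is considered reasonably or possibly related to the use of the investigational product". It neither defines *unexpected* nor refers to either definition above.

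Section C.9 reproduces adverse reactions from the Brochure in Tables 2 and 3, as terms with counts and percentages and no severity column. On the experience with Epidiolex and in previous studies, it adds: "The large majority of adverse events were mild to moderate and transient".

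**The concern.** The 7-day rule is confined to fatal and life-threatening events. In that group, one obvious way for an event to be new is that a known reaction appears in a far worse form. The general definition catches that case. The definition printed inside the 7-day rule does not mention it.

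The introduction to regulatory reporting in C.8 says that events meeting the criteria that follow are submitted as expedited reports. Staff working through those criteria will naturally use the definition they find there. If they do, a related fatal or life-threatening case of a listed reaction could be classed as expected. The FDA and the manufacturer would then learn of it later than the general definition implies, or not through an expedited report at all. The matter affects safety reporting only; no endpoint, estimand or analysis depends on it.

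**Working it through.** No arithmetic underlies this point apart from one difference between two time limits. The check is to set the definitions side by side, run test cases through them, and look for text that reconciles them.

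**Step 1: compare the definitions.**

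| | Unanticipated Adverse Events | 7-day rule | 15-day rule |
|---|---|---|---|
| Nature of the event counts | yes | yes, through the word *described* | not stated |
| Severity counts | yes, explicitly | not mentioned | not stated |
| Reference | the relevant source documents, unnamed | Investigator Brochure | not stated |
| Clock | none given | 7 calendar days | 15 calendar days |

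**Step 2: run test cases.** Each is a fatal or life-threatening event judged possibly related. For cases A to C, take the Brochure to be the relevant source document.

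- *Case A: the reaction is nowhere in the Brochure.* Unexpected under both definitions. No conflict.
- *Case B: the Brochure describes the reaction at that severity.* Expected under both. No conflict.
- *Case C: the Brochure lists the reaction, but only in a milder form.* Unexpected under the general definition, because the severity is inconsistent with the source. Under the literal 7-day wording the reaction is already described, so the event need not count as unexpected and the 7-day trigger need not be met. The definitions conflict.

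Sedation, which is in Table 2, shows how case C could arise. If the Brochure describes only milder sedation, a related life-threatening episode would be case C. If it describes life-threatening sedation, the same episode would be case B. The tables alone cannot say which.

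**Step 3: follow case C into the 15-day rule.**

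- If that rule takes the general definition, the event is serious, unexpected and related, and a written report is due within 15 days. The difference is then 15 − 7 = 8 calendar days between the two deadlines.
- If that rule takes the definition in the 7-day subsection, neither expedited report is triggered.

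The text supports neither choice over the other. The federal regulation cited in the 15-day subsection is invoked for the analysis of similar events, not for expectedness.

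**Step 4: compare the reference documents.** The general definition speaks of source documents without naming them, while the 7-day rule names the Brochure. The section on potential drug-drug interactions also cites a separate core safety information document dated August 2015. If that counts as a source document, the two subsections could also disagree about an event described in one document and not in the other.

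**Step 5: look for a reconciling sentence.** From the opening of C.8 to the end of C.9, no sentence says which definition governs, and neither definition cross-refers to the other.

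**The case against.** The strongest reply is that the 7-day rule should not be read in isolation. The general definition stands earlier in the same section, names severity, and itself speaks of expedited reporting. A careful investigator could also hold that a life-threatening form of a reaction listed only as mild is *not* already described, in which case the definitions agree. Section C.8 also says adverse events are classified by ICH GCP definitions, and section D commits the study to applicable regulatory requirements. Serious events are documented by the Sponsor-Investigator within 24 hours whether expected or not, and an ethics board and a data safety monitoring board oversee the trial.

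Much of this stands, and it limits the claim. A reader might infer that any mention of a term in the Brochure makes every form of it expected, or that a severe case would certainly go unreported. The documents support neither: the wording permits that outcome but does not compel it. A reader might also assume that the 15-day rule inherits the narrower definition. Nothing says so, and the general definition fits it at least as naturally.

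The reply does not remove the conflict. That two reasonable readers can classify the same death differently is the defect. The 24-hour step is internal documentation, not a report to the FDA. The example in the study stopping rules needs the same related event of grade 3 or higher in at least two subjects, so a first case does not meet it. What the outside standards say about expectedness cannot be checked from these documents.

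**Conclusion.** The point holds as a conflict between two stated rules. The 7-day rule, followed literally, need not be triggered by a related fatal or life-threatening case of a reaction that the Brochure lists only in a milder form, although the general definition in the same section would class that case as unexpected. The effect on the 15-day report is undetermined: a deadline 8 days later if that rule takes the general definition, no expedited report if it takes the narrower one.

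The number of events affected cannot be estimated. It is tempting to count every reaction in Tables 2 and 3 as falling in the gap, but that depends on how the Brochure describes severity, which cannot be seen here, and some listed terms, such as eructation or a product size issue, are not plausible as fatal or life-threatening reactions. Nor can the rate of drug-related serious events that section C.1 quotes from an epilepsy cohort be used. It counts all related serious events in a different, largely paediatric population, not those that are fatal or life-threatening and new only in severity.

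The conclusion assumes that the Brochure lists at least one reaction only in a form milder than life-threatening. The remark in C.9 that most events were mild to moderate makes this plausible but does not prove it. The correction is worth making: it is a small wording change, and it bears on when the regulator and the manufacturer hear of the gravest events.

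**What to change.** Use one definition of *unexpected* in all three subsections: an event is unexpected if the named reference safety document or documents do not describe it, or if its nature or severity departs from what is described there. State it once, under Unanticipated Adverse Events, and have the 7-day and 15-day subsections refer to it in place of the present 7-day definition and the present silence of the 15-day rule.

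Name the same reference document or documents throughout. Changing only the 7-day sentence would leave unnamed source documents in one place and the Brochure in another. If the separate core safety information is meant to count, say so; if only the Brochure is meant, say that.

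The cost is a sentence or two of protocol text and possibly a few more expedited reports. Design, dosing and analysis are unchanged.
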